## **Study design and description**

This work is designed as a randomized, sham-controlled clinical trial in which we monitor the effects of low-energetic focused shock wave therapy (ESWT) on Achilles (AT) tendinopathy. We estimate that at least 18 patients will participate in it. They will be randomly divided into two groups in 1:1 ratio. Group A will receive ESWT according to selected parameters (see below). Group B will receive placebo in the means of sham-ESWT (see below).

Patients in both groups will have same program. The research within one patient will last in total of 8 weeks from the initial to the end examination. In the initial week the patient will be clinically examined by a physiotherapist, an ultrasonography (USG) examination will be performed and VISA-A questionnaire will be filled. At the end of this session, the patient will be randomly assigned to group A or B and receive first application (ESWT or sham-ESWT). For the next 4 weeks, once a week, the next applications will be performed. The interval between individual applications should be at least 5 days. Thus, a total of 5 applications of ESWT or sham-ESWT will be performed. The final examination will be performed at 3 weeks follow up after the last application and includes the same procedures as in the initial examination.

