## **Patients distribution and randomization**

Patients will be randomly divided into two groups (Group A, Group B) in a 1:1 ratio. Patients in Group A will receive low-energetic focused ESWT according to selected parameters. Patients in Group B will receive placebo (sham-ESWT). The patients themselves will not know which group they are in. Before, during, and even after the session, patients will not be allowed to see the applicator or machine. The sham applicator will have to be always prepared before the patient come into the intervention room.

Due to the fact that AT tendinopathy includes a wider range of causes that can be monitored by USG examination, the finding on USG examination will also be taken into account when dividing into groups. In each group the specific cause should be represented in similar proportion. For this reason, the patient will be assigned to one of the groups only after the initial examination.

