## **Initial and final examination**

During the initial and final examinations, the several tasks to the patient will be performed. Firstly the anamnestic data will be collected, then the ankle dorsiflexion range of motion will be measured using the "weight-bearing lunge test" (cm). Thompson's test and resistance test will be

performed at the same time. The area of greatest pain will be localized by palpation. Then patient will also perform AT loading tests on both legs — single leg heel rise test and single leg hop test. The patient will perform as many heel rises/hops using only one leg as possible in 30 seconds or until first sign of pain in Achilles tendon area. This will be also measured in asymptomatic leg.

Secondly, the patient will be asked to complete a validated Victorian Institute of Sports Assessment - Achilles questionnaire, which assesses the subjectively perceived severity of the disease and partly its impact on the quality of normal daily or sports activities.

The patient's maximal pain will be assessed using a standardized numerical rating scale (NRS) of pain. The patient will be asked about the maximum pain that could be caused by various factors, at the initial examination, at the last application and during the final examination.

Lastly, the ultrasonographic examination of patient's AT in both legs will be performed. This examination is described in the following chapter.

Both, initial and final examinations in each patient will be performed by only one person (the investigator of the study) and the same person will prepare and perform each application of ESWT or sham-ESWT.

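### In the visible text no visit has a named side-effect question and no harms summary is planned, so transient reactions and a per-patient count by group are not captured

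*Combined protocol and SAP*

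**What the plan says.** The Study design and description section gives each patient five applications, active or sham. The first closes the initial session and the other four follow weekly. On spacing it says "The interval between individual applications should be at least 5 days". On the end of follow-up it says "The final examination will be performed at 3 weeks follow up after the last application", and that this visit "includes the same procedures as in the initial examination". The same section puts the total at 8 weeks from first to last examination.

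The Initial and final examination section opens with the history, "Firstly the anamnestic data will be collected", without saying what it covers. On pain it says "The patient will be asked about the maximum pain that could be caused by various factors". It sets this question at three time points: "at the initial examination, at the last application and during the final examination". No recall window is given. One investigator does both examinations, and "the same person will prepare and perform each application of ESWT or sham-ESWT".

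The Patients distribution and randomization section states blinding for patients: "patients will not be allowed to see the applicator or machine".

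Side effects are named once, in the Sham applicator section, as an expectation that the self-made modification will cause none. The Patient selection section excludes contraindications to shock wave treatment, which is screening and not collection of harms. The Data analysis section has no side-effect item. The one patient count it names is of those with pain during the loading tests.

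**The concern.** The trial compares an active device with a self-made sham over five exposures. A reader of the results will want to know how many patients in each group had a reaction. Followed as written, the plan does not produce that number.

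The gap cannot be repaired at analysis, because a short-lived reaction that nobody recorded is lost. There is also a practical side. The device settings are fixed for the whole study at 1300 shocks per application, and no written step asks about the previous application before the next one is given. The investigator may note what patients mention at weekly visits. Such notes would be unstructured and made by someone who prepares the applicator and so knows the group, which is a weak basis for comparing groups.

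**Working it through.** **What is written at each contact**

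- Initial session: history, lunge test, Thompson's and resistance tests, palpation, heel-rise and hop tests, VISA-A, pain scale and ultrasound, then randomisation and application 1. All of these measurements come before treatment.
- Applications 2, 3 and 4: the application only.
- Application 5: the application and the pain scale.
- Final examination: the initial procedures repeated.
- Data analysis: descriptive statistics of initial and final values; two-way ANOVA with Tukey for most parameters; paired t or Wilcoxon tests within each group; loading tests described only, with the count of patients who had pain in them.

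The pain scale may register a flare, but it asks about pain from any cause and does not cover non-pain reactions. Its application-5 value is neither an initial nor a final value, so it has no named place in the analysis. Pain in the loading tests is a symptom of the disease under treatment. The repeated ultrasound and clinical tests can show what is still present three weeks after treatment ends, but not what came and went before.

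**Recall if the final history does ask**

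Inputs: five applications, weekly, final visit 21 days after the fifth. On that schedule the recall for application k is (5 − k) × 7 + 21 days:

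- k = 1: 4 × 7 + 21 = 49
- k = 2: 3 × 7 + 21 = 42
- k = 3: 2 × 7 + 21 = 35
- k = 4: 1 × 7 + 21 = 28
- k = 5: 21

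Application 1 is given at the initial session, so its recall equals the whole study length. The stated total of 8 weeks gives 8 × 7 = 56 days. The range for application 1 is therefore 49 to 56 days.

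The 5-day minimum gap taken alone would give 4 × 5 + 21 = 41 days. That places application 5 on day 20, whereas one application in each of the four following weeks (days 1–7, 8–14, 15–21, 22–28) places it on day 22 at the earliest, and 22 + 21 = 43. The figure of 41 does not fit the weekly schedule and is not used.

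With a form before each of applications 2 to 5, nominal recall for applications 1 to 4 becomes 7 days (5 at the shortest permitted gap; no longest gap is stated). For application 5 it stays at 21 days.

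**What 9 patients per group can show**

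The minimum of 18 patients in a 1:1 ratio gives 9 per group. The documents give no reaction rate, so the rates here are an assumed range.

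- Upper one-sided 95% limit for 0 of 9: 1 − 0.05^(1/9) = 0.283.
- Chance of at least one affected patient among 9, 1 − (1 − p)^9: 0.370 at p = 5%, 0.613 at 10%, 0.866 at 20%, 0.960 at 30%.

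A common reaction would probably appear at least once if patients are asked. An empty column would not show safety.

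**The case against.** The strongest reply is that the plan does look for harm. The final examination repeats palpation, Thompson's and resistance tests, VISA-A, the pain scale and ultrasound of both tendons, including continuity, bursa, calcification, Doppler signal and thickness. Most measured parameters are tested against baseline within each group, the sham group included. This stands. A reader might infer that harms go wholly unexamined, or that the expectation about the sham is never put to any check. The documents do not support that: lasting structural or functional worsening could show in either group.

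A second reply is that the finding rests on absence. The opening part of the document, any consent pages and the design graphic were not available, and a harms procedure could be there. This also stands, so the point is limited to the visible text.

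A third reply is that a symptom form cannot attribute a complaint to treatment any better than the pain scale can, since a painful tendon fluctuates anyway. This is correct. Such a table must not call its entries side effects. Its value lies in timely, structured collection by group.

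A fourth reply is low yield: the numbers are small, and weekly questions may lead patients to guess their group in a trial where patients are the only people stated to be blinded. The risk is real but small, and identical, neutral forms reduce it without removing it. The low yield limits what may be concluded from the table; it does not justify leaving the question unasked.

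**Conclusion.** The point holds in a limited form. In the visible text no visit has a named side-effect question, three of the five applications have no written assessment, and no harms summary is planned. What is lost is transient reactions between visits and a per-patient count by group. Lasting worsening could still be seen at the final examination. If the unspecified final history does ask, a reaction to application 1 is recalled after 49 days on the weekly schedule, or up to 56 under the stated total.

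A reader might also infer that the efficacy comparison is compromised or that the trial should be larger. Neither follows: no efficacy endpoint, planned test or sample size depends on this. With 9 per group any harms table is descriptive, since 0 of 9 remains compatible with a rate of 28%.

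The conclusion assumes that the unavailable parts contain no harms procedure and that the minimum size of 18 is what is recruited. It is a cheap improvement that should be made before recruitment, because it changes what is collected.

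**What to change.** In the Study design and description and the Initial and final examination sections, add a short form before each of applications 2 to 5 and at the final examination. The patient completes it, and it is identical in both groups. In neutral wording that suggests no particular reaction, it asks for any new or worse symptom since the last visit, at the treated site or elsewhere, and when it began relative to the last application. The form is read before the next application is given.

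In the Data analysis section, add one descriptive table by group of patients reporting any new or worse symptom, labelled as symptoms regardless of cause, with no significance test. If the design graphic or an unavailable page already lists such a question, write it into these sections and add the table.

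Cost: 5 forms × 18 patients = 90 forms. At an assumed 2 minutes each this is 180 minutes, or 3 hours in total (1.5 hours at 1 minute, 7.5 hours at 5 minutes), at visits that already take place and with no extra staff. The remaining drawbacks are the small risk to patient blinding and the unchanged 21-day recall for application 5.

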### **Ultrasonographic examination**

USG examination will be performed with a Mindray DC-70 machine with a linear probe type L12-3E with a frequency of 12 Hz in the preset "MSK" mode. The whole area of AT will be monitored from the connection of soleus fibers to the insertion site on the calcaneus by longitudinal and transverse imaging.

The echotexture and continuity of the tendon, the echotexture of KFP, the presence of RC bursa, calcifications and osteophytes will be evaluated visually. At the same time, the possible degree of vascularization in or around the tendon will be evaluated using Doppler mode.

The values of anteroposterior tendon width, paratenon thickness, and CSA at the anteroposterior widest point will be collected using the measuring instruments included in USG machine.

USG findings will be consulted and evaluated in cooperation with an expert in USG diagnostics to increase their relevance and reduce the error rate.

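### The scan follows loading tests that stop at pain, with no set rest, so an acute loading effect of unknown size (possibly zero) could mix with structural change in the ultrasound outcomes

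*Combined protocol and SAP*

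**What the plan says.** The section Initial and final examination gives an explicit sequence. History, lunge test, Thompson and resistance tests and palpation come first. The next step is "Then patient will also perform AT loading tests on both legs". The amount of loading is not fixed: the patient performs "as many heel rises/hops using only one leg as possible in 30 seconds or until first sign of pain". The questionnaire follows ("Secondly, the patient will be asked to complete a validated Victorian Institute of Sports Assessment - Achilles questionnaire"), then the pain rating, and the scan closes the session: "Lastly, the ultrasonographic examination of patient's AT in both legs will be performed".

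The section Study design and description lists the steps more briefly: "the patient will be clinically examined by a physiotherapist, an ultrasonography (USG) examination will be performed", with the questionnaire named after the scan ("an ultrasonography (USG) examination will be performed and VISA-A questionnaire will be filled"). The two sections therefore disagree on whether the scan precedes VISA-A. Neither places the scan before the clinical examination. The final visit repeats the procedures of the initial visit.

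The section Ultrasonographic examination collects anteroposterior width, paratenon thickness and CSA, and adds that "the possible degree of vascularization in or around the tendon will be evaluated using Doppler mode". Data analysis treats the repetition counts descriptively only and plans no adjustment of the ultrasound values for them. No section sets a rest period before the scan.

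**The concern.** The loading before the scan is set by pain. A patient who stops at the first painful hop does a few cycles, while one without pain does the full time on each test. A patient whose pain improves between visits may therefore load the tendon more before the final scan than before the initial one.

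Suppose ESWT relieves pain more than sham, and suppose loading leaves a measurable trace until the scan. The group difference in ultrasound change would then combine two things: lasting structural change, which the trial wants to measure, and a short-lived response to the test. The sign is not fixed either. A Doppler signal raised by longer hopping, for example, would count against the treatment.

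Keeping the same order at both visits removes only the part of the effect that is constant within a patient. It leaves the part that moves with pain. The opposite leg is not an unloaded reference, because it does the same tests.

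**Working it through.** **Step 1: order and load (from the documents).**

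| Item | Initial and final examination | Study design and description |
|---|---|---|
| Loading tests | first block, after palpation | not named separately; within the clinical examination |
| VISA-A | after loading, before the scan | named after the scan |
| Scan | last | after the clinical examination |
| Rest before the scan | none stated | none stated |
| Load | up to 30 s or first pain | not stated |

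Both descriptions put the scan after the loading. Only the first does so in explicit steps. The second is a short list and is weaker evidence of order.

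**Step 2: what a bias would require.** Two conditions must both hold:

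- Up to 30 seconds of each test changes the ultrasound values, and the change lasts until the scan.
- The groups differ in how much their repetitions change from the initial to the final visit.

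The documents give no figure for either. If either fails, the expected bias in the group comparison is zero.

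**Step 3: illustration.** The plan has no figure of its own to reproduce here. Inputs:

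- From the documents: at least 18 patients, 1:1, so 18 / 2 = 9 per group.
- Assumed: tendon width 8 mm; acute change after a full bout 0 to 5%, that is 0 to 0.05 x 8 = 0.4 mm; SD of the change score 0.3 to 0.5 mm; two-sided alpha 0.05; no true structural effect.
- Assumed, extreme case: Group A goes from 40% to 90% of a full bout and Group B from 40% to 50%. The gap in change is (90 - 40) - (50 - 40) = 40 percentage points.

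Spurious shift b = acute change x gap. A two-sample t-test on change scores (16 degrees of freedom, critical value 2.12) stands in for the planned ANOVA. Its non-centrality is (b / SD) x sqrt(9/2).

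| Case | b | Non-centrality, SD 0.3 / 0.5 mm | Rejection rate, SD 0.3 / 0.5 mm |
|---|---|---|---|
| No acute effect or no gap | 0 mm | 0 / 0 | 5.0% / 5.0% |
| Acute effect and gap both halved | 0.2 x 0.2 = 0.04 mm | 0.28 / 0.17 | 5.8% / 5.3% |
| One of them halved | 0.2 x 0.4 = 0.08 mm | 0.57 / 0.34 | 8.3% / 6.2% |
| Extreme case | 0.4 x 0.4 = 0.16 mm | 1.13 / 0.68 | 18.6% / 9.8% |

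**Step 4: the same check in SD units.** Let a be the acute effect of a full bout in SDs of change, and f the gap as a fraction. With a = 0.25 and f = 0.25, the shift is 0.06 SD and the rejection rate 5.2%. With a = 0.5 and f = 0.5, it is 0.25 SD and 7.9%. With a = 1.0 and f = 0.5, it is 0.50 SD and 17.0%. The result runs from nothing to material, and the documents cannot place the trial within that range. No size is worked out for Doppler, because the documents give no scale for it.

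**The case against.** The strongest objection is that the mechanism is unproven. No section says that tendon dimensions or Doppler signal respond to half a minute of heel rises or hops. In the fuller description, the questionnaire and pain rating fall between loading and scan, which gives some time for any effect to fade. This stands. A reader might infer that acute changes do enter the final values, and unequally between groups. The documents do not support that reading, because they establish neither condition in Step 2.

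Second, the inflation depends on a real difference in pain. If ESWT changes neither pain nor repetitions relative to sham, randomization balances the loading in expectation. Patient blinding and a sham matched for sound, duration and skin sensation make expectation a weak driver of a group difference. This also stands. However, a difference in pain is what would be expected if the treatment works, so the problem would arise when the ultrasound result is of most interest.

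Third, a reader might take 10 to 19% as the likely size. It is the extreme corner of assumed inputs, and halving one or both of them gives 5.3 to 8.3%. The plan admits patients whose limitation is only partial. Some may already complete 30 seconds at the initial visit and have no room to increase.

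Fourth, moving the scan to the very start of the visit would show the single investigator the lesion before palpation for the most painful area. That is a fair objection to a wider reordering, and nothing here argues that the lunge, resistance or palpation steps disturb the scan. The change should be limited to the two loading tests.

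**Conclusion.** The concern holds as a gap in standardisation, not as a demonstrated bias. The plan lets the load before each scan vary with pain and neither controls it nor adjusts for it. An acute effect of unknown size, possibly zero, could therefore mix with structural change in width, CSA, paratenon thickness and Doppler signal if ESWT relieves pain more than sham. If it does not, the order adds noise only to the group comparison.

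At 9 per group, the illustrated false-positive rate is 5% with no shift, 5 to 8% for 0.04 to 0.08 mm, and 10 to 19% in the extreme case. Every input other than the group size is assumed. The point is a cheap improvement. It should be settled before data collection, because later adjustment for repetitions would condition on a variable measured after treatment, with about 18 patients.

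**What to change.** In both Study design and description and Initial and final examination, state one order for both visits: history, lunge test, Thompson and resistance tests, palpation, the same short rest, the ultrasound and Doppler scan, and only then the heel-rise and hop tests. Reconcile the order of the scan and VISA-A so that the two sections agree.

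This takes the visit's own loading tests out of the scan conditions whatever their true effect, and keeps palpation ahead of the scan. It costs a few extra minutes per visit and no additional staff, visit or procedure. The one drawback is that the investigator will have seen the scan before running the loading tests. This matters little, because those tests are analysed only descriptively.

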### **Ultrasonographic examination**

USG examination will be performed with a Mindray DC-70 machine with a linear probe type L12-3E with a frequency of 12 Hz in the preset "MSK" mode. The whole area of AT will be monitored from the connection of soleus fibers to the insertion site on the calcaneus by longitudinal and transverse imaging.

The echotexture and continuity of the tendon, the echotexture of KFP, the presence of RC bursa, calcifications and osteophytes will be evaluated visually. At the same time, the possible degree of vascularization in or around the tendon will be evaluated using Doppler mode.

The values of anteroposterior tendon width, paratenon thickness, and CSA at the anteroposterior widest point will be collected using the measuring instruments included in USG machine.

USG findings will be consulted and evaluated in cooperation with an expert in USG diagnostics to increase their relevance and reduce the error rate.

### **ESWT application**

[figure not shown]
The focused ESWT will be applied to patients in Group A from the BTL-6000 FSWT device with a penetration depth modulating len for the treatment of superficial structures. Energy Flux Density will be set in the low-mid energy spectrum to 0.12 mJ / mm^2, frequency 10 Hz, with a total number of shocks of 1300. The application will be performed semi-statically using an USG gel in the area of the largest USG finding. Of the total numbers of shocks, 500 shocks will be applied from both sides of the AT, then 300 shocks from the dorsal side of the tendon will be applied as well. The set values will not change throughout the study.

